## 9. MEASUREMENT OF EFFECT

### 9.1 Primary endpoint:

The primary endpoint is measured by PSA level. Patients achieving a PSA level  $\leq 0.2$  ng/ml at the end of six cycles of enzalutamide and EBRT treatment are considered successes.

### 9.2 Secondary endpoints

#### 9.2.1. Safety and Tolerability

Safety and tolerability will be documented throughout the study by assessment of adverse events, vital signs and laboratory assessments as defined in the Schedule of Activities (Section 8). Adverse events will be graded according to the National Cancer Institute Common Terminology Criteria for Adverse Events, Version 4.03 (NCICTCAE v4.03). Only toxicity with attribution of possibly, probably or definitely ('treatment-related') will be reported. Adverse events will be monitored and recorded until the safety follow-up visit (3 months after the completion of the drug therapy). Any glucose tests collected under previous protocol amendments will not be assessed for adverse events.

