### 1.3 Secondary Objectives

1. Assessment of the effect of treatment on health-related quality of life including fatigue, sleep quality, as well as urinary, bowel, sexual and hormonal functioning.
2. Assessment of the effect of treatment on serum sex hormones including androgens and estrogens.
3. Assessment of the effect of treatment on body fat distribution and muscle mass.
4. Assessment of safety and tolerability according to adverse event reporting during the trial.
5. Assessment of the effect of treatment on bone metabolism.

CONFIDENTIAL

This document is confidential. Do not disclose or use except as authorized.

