## **5.4 Duration of Therapy**

**5.4.1** Enzalutamide - 6 (28 +/-3 days) cycles-expected

**5.4.2** External beam radiation up to 11 weeks-expected

**5.4.3** Treatment will continue for 6 (28 day) cycles or until one of the following criteria applies:

- Disease progression;
- Intercurrent illness that prevents further administration of treatment;
- Unacceptable adverse event(s);
- Participant demonstrates an inability or unwillingness to comply with the oral medication regimen and/or documentation requirements;
- Participant decides to withdraw from the study; or
- General or specific changes in the participant's condition render the participant unacceptable for further treatment in the opinion of the treating investigator.

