#### **10.1.4 Attribution**

Attribution is the relationship between an adverse event or serious adverse event and the study treatment. Attribution will be assigned as follows:

- Definite – The AE is clearly related to the study treatment.
- Probable – The AE is likely related to the study treatment.
- Possible – The AE may be related to the study treatment.
- Unlikely - The AE is doubtfully related to the study treatment.
- Unrelated - The AE is clearly NOT related to the study treatment.

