### **10.2 Procedures for AE and SAE Recording and Reporting**

Participating investigators will assess the occurrence of AEs and SAEs at all participant evaluation time points during the study.

All AEs and SAEs whether reported by the participant, discovered during questioning, directly observed, or detected by physical examination, laboratory test or other means, will be recorded in the participant's medical record and on the appropriate study-specific case report forms.

The descriptions and grading scales found in the revised NCI Common Terminology Criteria for Adverse Events (CTCAE) version 4.0 will be utilized for AE reporting. All appropriate treatment areas should have access to a copy of the CTCAE version 4.0.

A copy of the CTCAE version 4.0 can be downloaded from the CTEP website at:

[http://ctep.cancer.gov/protocolDevelopment/electronic\\_applications/ctc.htm](http://ctep.cancer.gov/protocolDevelopment/electronic_applications/ctc.htm).

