## 13.2 Analysis of Secondary Endpoints

### 13.2.1 Health related quality of life

The primary HRQoL aim is to assess the change from baseline to the end of cycle 6 in the vitality or hormonal function score as well as the sexuality score on the EPIC-26 questionnaire. It is anticipated approximately 75% of patients will have both scores for each domain. A one-sample t-test will be used to assess the overall change in score. To be considered a clinically meaningful difference will be defined as half historical standard deviation for the specific domain. Given 48 evaluable patients, there is 80% power to detect a 0.41 change in the hormonal domain score of the EPIC-26 assuming 2-sided 5% alpha. Results in this study will be evaluated in the context of past research by Sanda et al showing patients that received radiotherapy with non-hormonal therapy had a score on the vitality or hormonal function domain of approximately 80 and a score on the sexuality domain of 26.

Descriptive statistics at each time point and changes over time will be provided for each of the EPIC-26 domains as well as for the PROMIS-Fatigue and PSQ1. Mixed models will be used to explore the impact of time on quality of life adjusting for prognostic baseline factors.

13.2.2 Safety and Tolerability: We will monitor toxicities experienced by all treated patients. Frequency and severity of worst grade 3 or higher treatment-related AEs by type will be reported along with the incidence of overall grade 3 or higher treatment-related AEs. With 71 treated patients, the maximum width of a 90% CI for a given toxicity is 21%. The probability of observing one rare severe toxicity (true rate=5%) is 97%. Tolerability endpoints include the number of dose reductions and treatment interruptions as well as the number of patients that discontinue treatment due to AEs. The safety summary will include clinical laboratory, ECG and vital signs data.

13.2.3 Hormone Levels: Descriptive statistics at each time point and changes over time will be provided for all hormone measures. Paired t-tests and two-sample t-tests (or non-parametric equivalents) will be used to assess significance of change over 6 cycles of treatment in hormone levels for the overall cohort and by status on primary clinical endpoint (yes or no achieving PSA level  $\leq 0.20$  ng/ml at the end of 6 cycles of treatment with enzalutamide and EBRT).

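### The plan reports only treatment-related adverse events, with no all-cause table, and the calendar's AE row is blank at the 3-month visit where the text requires recording

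*Combined protocol and SAP*

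**What the plan says.** All places are in the combined protocol and SAP.

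- **Objective.** Secondary objective 4 (1.3) is "Assessment of safety and tolerability according to adverse event reporting during the trial".
- **Collection.** 10.1.1 counts an event as an AE whether or not it is thought related. 10.2 requires that every AE and SAE, however detected, be entered in the medical record and "on the appropriate study-specific case report forms". It also says "Participating investigators will assess the occurrence of AEs and SAEs at all participant evaluation time points during the study".
- **Attribution.** 10.1.4 uses five categories: definite, probable, possible, unlikely and unrelated.
- **Reporting rule.** 9.2.1: "Only toxicity with attribution of possibly, probably or definitely ('treatment-related') will be reported".
- **Specified AE tables.** 13.2.2: "Frequency and severity of worst grade 3 or higher treatment-related AEs by type will be reported", together with the overall incidence of the same class of event. 13.2.2 also counts dose reductions, interruptions and discontinuations due to AEs, and adds laboratory, ECG and vital-sign summaries.
- **Timing.** 6.3.1 collects AEs from first dose to the final study visit. 9.2.1 records them to the safety visit 3 months after drug therapy and points to Section 8 for the schedule. In Section 8, the row that combines AEs and concomitant medication is blank in the 3-month column.

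**The concern.** The plan collects AEs without regard to cause but reports them through a causality judgement. With no control arm, nothing in the trial can test that judgement. Events rated unlikely or unrelated stay in the database and enter no specified AE table, so a reader cannot tell how many there were or of what kind.

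This matters because tolerability is central to the trial's rationale. Section 2.3 hopes for anti-tumor effects similar to LH-RH agonists without castration-type toxicity, and 1.1 says convincing data would lead to a randomized phase III trial. Several effects listed as common in 6.1.3 (flushing, fatigue, arthralgia, gynecomastia) may well be low grade, and no AE table is specified for grades 1 and 2.

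The calendar issue is separate. The 3-month visit is the only scheduled visit after treatment ends. A site working from the calendar and a site working from 9.2.1 would have different instructions for it.

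**Working it through.** **1. The plan's own safety figures.** Input: 71 treated patients (13.2.2). The plan says "The probability of observing one rare severe toxicity (true rate=5%) is 97"%.

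- P(at least one event) = 1 − (1 − 0.05)^71 = 1 − 0.026 = 0.974, which matches 97%. The figure is for at least one event; exactly one would be 0.098.
- The maximum width of an exact (Clopper-Pearson) 90% interval over 0 to 71 events is 0.206, which matches the stated 21%.

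Both figures reproduce, and the point below changes neither.

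**2. What is recorded against what is reported.**

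| Step | Section | Attribution | Grade |
|---|---|---|---|
| Definition | 10.1.1 | any | any |
| CRF recording | 10.2 | any | any |
| Reporting rule | 9.2.1 | three of the five categories | no limit stated |
| Two AE tables | 13.2.2 | treatment-related only | 3 or higher |
| Count of discontinuations due to AEs | 13.2.2 | no limit stated | no limit stated |

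The attribution limit comes from 9.2.1. The grade limit comes only from the tables in 13.2.2.

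**3. Direction of the effect.** Let T be the AEs recorded and U those rated unlikely or unrelated. The number eligible for reporting is R = T − U. So R ≤ T, with equality only if U = 0. The filter can lower the counts but never raise them. The documents give no value or expected range for U/T and do not plan to report U, so the size cannot be computed.

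**4. The calendar.** Section 8 has ten visit columns. The AE row is marked at baseline, day 1 of cycles 2 to 6, and end of cycle 6: 1 + 5 + 1 = 7 marks. The 3-month cell is blank. In that same column, history and examination, vital signs, blood count, chemistry, bone markers, PSA and quality of life are all marked. The history and examination row fills the column correctly, so the blank AE cell is not a shift in the table.

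**5. The time windows side by side.**

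- 6.3.1: AEs collected to the final study visit.
- 9.2.1: AEs recorded to the 3-month visit.
- 5.5.1: patients remain on study for 3 months after enzalutamide stops.
- Section 8: last AE mark at end of cycle 6.
- 10.4.1: SAE reporting to 30 days after the last dose.
- 10.8: AEs arising up to 30 days after the last intervention are followed to resolution.
- 5.3.1.1: concomitant medication to 30 days after the last dose.
- 11.1.2: the Adverse Event Report Form is due by cycle. A Follow up/Survival Form is due after the follow-up visit, but its contents are not stated.

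Taking 3 months as about 90 days, the text in 6.3.1 and 9.2.1 reaches about 90 − 30 = 60 days beyond the 30-day windows.

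**The case against.** The strongest reply is that the rule is pre-specified and open, that its threshold begins at possible relation, and that the trial is exploratory with safety as one of five secondary objectives. Recording and reporting are different acts, so 10.2 and 9.2.1 do not contradict each other. An all-cause table in one arm has no comparator. All of this is true. It shows that the rule is deliberate and limits how the added table can be read. It does not answer the point that readers cannot see what the rule removes.

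Other sources narrow the gap:

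- SAEs are reportable regardless of causality (10.1.2, 10.4.1), and the safety committee reviews toxicity (11.2).
- 13.2.2 counts discontinuations due to AEs with no stated attribution limit, and summarizes laboratory and vital-sign data.
- Section 8 grades breast enlargement at three time points and asks about breast symptoms at every study visit.
- EPIC-26 item 13 covers hot flashes, breast tenderness or enlargement, and lack of energy.

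These pick up several expected low-grade effects without an attribution step. None of them is an all-cause AE table.

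On the calendar, 6.3.1 and 9.2.1 are explicit, an examination and laboratory tests are scheduled at 3 months, and a follow-up form exists. The blank may simply reflect a row shared with concomitant medication, whose window is shorter. That is a plausible explanation, and it supports splitting the row.

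**Conclusion.** The point stands as a reporting gap plus a scheduling inconsistency. Under 9.2.1, reported AE counts can only equal or fall short of recorded counts. The two AE tables in 13.2.2 omit events rated unlikely or unrelated, and all grade 1 and 2 events. The size of the shortfall is unknown. No sample size, error rate or precision figure is affected. The conclusion rests on reading 9.2.1 as written, and on there being no all-cause summary elsewhere in the documents; none was found.

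A reader might infer more than this. The documents do not support these readings:

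- **That related grade 1 and 2 events are barred from reporting.** 9.2.1 sets no grade limit. A summary of them is unspecified, not excluded.
- **That the 97% detection figure is overstated.** This would need the 5% to be an all-cause rate and an assumed share of events to be filtered out. The figure directly follows the treatment-related tables, and the documents give no such share.
- **That giving radiation during enzalutamide makes wrongful exclusion more likely.** 10.1.4 says "Attribution is the relationship between an adverse event or serious adverse event and the study treatment". If that term covers both treatments, an event possibly due to either passes the filter. Separating the two causes is a different problem, which an all-cause table would not solve.
- **That the blank AE cell at fiducial placement is a second contradiction.** The only mark in that column is the optional tissue sample, so it is not clearly an evaluation time point under 10.2.
- **That late events will be lost.** The text requires them to be recorded. What is established is that the calendar disagrees with the text.

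**What to change.** **Reporting.** In 9.2.1 and 13.2.2, tabulate all recorded AEs by type and worst grade, all grades, regardless of attribution. Keep the treatment-related grade 3 or higher table as a subset.

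**Schedule and forms.**

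- In Section 8, give AEs and concomitant medication separate rows, since the medication window in 5.3.1.1 ends at 30 days, and mark AE assessment at the 3-month visit.
- In 11.1.2, say whether AEs from that visit go on the Adverse Event Report Form or the Follow up/Survival Form.
- Reconcile the 3-month recording period with the 30-day windows in 10.4.1 and 10.8. These may serve different purposes (SAE reporting, and follow-up to resolution); if so, the text should say so.

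**Cost.** One further table from data already on the CRF, plus wording for a visit that already includes history, examination, laboratory tests and quality of life. No visit or sample size changes. The downside is a longer safety table that includes background events and cannot be read comparatively without a control arm; a sentence saying so should accompany it.

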### **2.3 Rationale**

Presently most patients with intermediate risk prostate cancer receive neoadjuvant, concurrent and adjuvant hormonal therapy with external beam irradiation. Multiple studies have shown that the addition of HT improves survival to external beam radiation (5,6) However androgen deprivation induced by LH-RH agonists consistently results in hot flashes, loss of libido, loss of sexual functioning, weight gain, changes in metabolism, loss of muscle mass and fatigue (7, 8).

In contrast, treatment with the anti-androgens bicalutamide or flutamide has minimal side effects, likely related to the fact that these agents do not suppress serum testosterone. Enzalutamide has the potential to have similar anti-tumor effects as LH-RH agonist without the toxicity associated with castrate testosterone levels. If it were shown that enzalutamide (enzalutamide) could be used as an effective adjuvant treatment for prostate cancer without androgen deprivation it would have dramatic and significant impact, including expanding its use to those patients who may have more intermediate risk and/or are unable to tolerate the toxicities associated with androgen deprivation

We have chosen as the primary endpoint the assessment of the proportion of patients whose PSA level is  $\leq 0.2$  ng/ml at the conclusion of therapy. This endpoint was chosen because patients that

CONFIDENTIAL

This document is confidential. Do not disclose or use except as authorized.

Version 13.0 Protocol Version Date: 1/09/2015

achieve this value after treatment with LHRH analogs in combination with EBRT have an excellent prognosis compared to patients that demonstrate higher PSA levels (1, 9). Furthermore, demonstration of PSA levels of  $\leq 0.2\text{ng/ml}$  in a significant number of patients treated on this study would be strong motivation to perform a phase III randomized trial comparing enzalutamide to LHRH analog therapy in the same setting.

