## 8.0 STUDY CALENDAR

	Screening (4 week period)	Baseline (Day One Cycle 1) 5+/- 3 day	At fiducial placement (3-7 weeks) (Study) (+/- 3 day)	Cycle 2, Day One (+/- 3 day)	Cycle 3, Day One (+/- 3 day)	Cycle 4, Day One (+/- 3 day)	Cycle 5, Day One (+/- 3 day)	Cycle 6, Day One (+/- 3 day)	End of cycle 6 (+/- 3 day)	3  months after completion of cycle 6
Hx/PE	X	X		X	X	X	X	X	X	X
Vital signs	X	X		X	X	X	X	X	X	X
Height/weight 		X		X	X	X	x	x	x	
CBC with diff	X	X		X	X	X	X	X	X	X
Chemistry/LFTs 	X	X		X	X	X	X	X	X	X
Bone Metabolism markers 		X							X	X
PSA	X	X		X	X	X	X	X	X	X
Hormonal measurements 	X 11	X					X		X	
Anthropomorphic measurements  and waist circumference		X							X	
Prostate tissue samples (optional)			X							
Q of L assessment 		X			X		X		X	X
Dispense med/Pill diary		X		X	X	X	X	X	X 7	
Adverse event and con med		X		X	X	X	X	X	X	
EBRT				X 8	X 					
Sign Informed Consent	X									
EKG	X									
Assessment of breast enlargement 		X		*	*	X	*	*	X	

- 1 -bone specific alk phos, serum C-teleopeptide, serum N terminal propeptide of type I collagen (fasting)
- 2- DHEA sulfate, estrogen (estradiol), free testosterone, total testosterone, estrone, androstenedione. These should be done while fasting.
- 3 -Triceps skin fold, biceps (mid-upper arm circumference), shoulder blade and waist. Height will only be necessary at the baseline visit.
- 4- EPIC-26, PROMIS, PSQI
- 5 -Any time between Day -7 to day 1
- 6- +/- 7 days
- 7- Collect pill diary and unused drug
- 8 - EBRT 7-10 weeks after initiating enzalutamide. This could fall on cycle 2 or 3.
- 9 -Chemistries includes: creatinine, BUN, potassium, sodium, bicarbonate LFT's include AST, ALT, total bilirubin and alkaline phosphatase.
- 10- Assessment will be done with calipers. The maximum diameter of the larger breast (if there is asymmetry) at Baseline (Day One Cycle 1), Cycle 4/day 1, End of Cycle 6 and assess it according to these parameters: grade 1 (<=2cm), grade 2 (>2-<=4cm), grade 3 (>4-6cm), and grade 4 (>6cm).
- 11- At screening visit, the only hormonal test required is total testosterone which will not require morning collection or fasting.\* We will ask you to answer a yes or no about breast tenderness and/or enlargement at every study visit.

CONFIDENTIAL

This document is confidential. Do not disclose or use except as authorized.

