## 10. ADVERSE EVENT REPORTING REQUIREMENTS

### 10.1 Definitions 10.1.1 Adverse

Event (AE)

An adverse event (AE) is any undesirable sign, symptom or medical condition or experience that develops or worsens in severity after starting the first dose of study treatment or any procedure specified in the protocol, even if the event is not considered to be related to the study.

Abnormal laboratory values or diagnostic test results constitute adverse events only if they induce clinical signs or symptoms or require treatment or further diagnostic tests. **10.1.2 Serious adverse event (SAE)**

A serious adverse event (SAE) is any adverse event, occurring at any dose and regardless of causality that:

- Results in death

CONFIDENTIAL

This document is confidential. Do not disclose or use except as authorized.

- Is life-threatening. Life-threatening means that the person was at immediate risk of death from the reaction as it occurred, i.e., it does not include a reaction which hypothetically might have caused death had it occurred in a more severe form.
- Requires or prolongs inpatient hospitalization (i.e., the event required at least a 24-hour hospitalization or prolonged a hospitalization beyond the expected length of stay). Hospitalization admissions and/or surgical operations scheduled to occur during the study period, but planned prior to study entry are not considered SAEs if the illness or disease existed before the person was enrolled in the trial, provided that it did not deteriorate in an unexpected manner during the trial (e.g., surgery performed earlier than planned).
- Results in persistent or significant disability/incapacity. Disability is defined as a substantial disruption of a person's ability to conduct normal life functions.
- Is a congenital anomaly or birth defect; or
- Is an important medical event when, based upon appropriate medical judgment, it may jeopardize the participant and require medical or surgical intervention to prevent one of the outcomes listed above. Examples of such medical events include allergic bronchospasm requiring intensive treatment in an emergency room or at home; blood dyscrasias or convulsions that do not result in inpatient hospitalization, or the development of drug dependency or drug abuse.

Events **not** considered to be serious adverse events are hospitalizations for:

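### Section 9.2.1 exempts glucose results already collected from adverse event assessment, which conflicts with Sections 10.1.1 and 10.2 for any value that caused symptoms or needed treatment or further tests

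*Combined protocol and SAP*

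**What the plan says.** The sentence on glucose closes Section 9.2.1 (Safety and Tolerability): "Any glucose tests collected under previous protocol amendments will not be assessed for adverse events". It is current protocol text, not an entry in a change log. No reason, grade limit or exception accompanies it.

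Four other places bear on it:

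- **Section 10.1.1**, the definition of an adverse event: "Abnormal laboratory values or diagnostic test results constitute adverse events only if they induce clinical signs or symptoms or require treatment or further diagnostic tests".
- **Section 10.2**: all adverse events, including those "directly observed, or detected by physical examination, laboratory test or other means, will be recorded in the" medical record and on the case report forms.
- **Section 8, footnote 9**: "Chemistries includes: creatinine, BUN, potassium, sodium, bicarbonate", followed by four liver tests. Glucose is not listed, nor is it in the bone or hormone panels of footnotes 1 and 2.
- **Section 13.2.2**: treatment-related events of grade 3 or higher are tabulated, and the safety summary is to contain clinical laboratory data. No exception for glucose is made there.

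Section 2.3 supplies the context. It says that androgen deprivation with LH-RH agonists "consistently results in hot flashes, loss of libido, loss of sexual functioning, weight gain, changes in metabolism, loss of muscle mass and fatigue", and hopes for a similar anti-tumour effect "without the toxicity associated with castrate testosterone levels".

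**The concern.** Dropping a test from future visits is an ordinary design choice. Exempting results already in hand from adverse event assessment is different: it makes ascertainment depend on the analyte, and it applies after the data exist. In a single-arm trial no control group would reveal the gap.

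Safety by adverse event reporting is the fourth secondary objective in Section 1.3, and metabolic change is among the LH-RH agonist effects that the rationale sets against enzalutamide. If a man's glucose result led to treatment or work-up and was then left unassessed, the absence of that event from the report would reflect the rule and not the drug. Such an event also could not reach the monitoring committee as an adverse event through that laboratory result. Section 11.2 says that the committee may be given unexpected events of grade 2 or higher that have been reported.

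**Working it through.** **Step 1. Where the rules collide.** Each kind of glucose finding is set against the three rules.

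| Finding | Section 10.1.1 | Section 10.2 | Section 9.2.1 | Conflict? |
|---|---|---|---|---|
| Abnormal value; no symptoms, treatment or further test | Not an adverse event | Nothing to record | Not assessed | No |
| Abnormal value that caused symptoms or needed treatment or further tests | Adverse event | Record | Not assessed | Yes |
| Hyperglycaemia found by history, examination or another route | Adverse event if symptoms, treatment or further tests apply | Record | Silent | No |

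Only the second row is a contradiction. Section 10.1.1 also requires onset or worsening after the first dose or a protocol procedure, so a value taken before then serves only as a baseline.

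**Step 2. Whether other glucose data could fill the gap.** The current calendar schedules no glucose, so no further protocol results are planned. Section 9.2.1 speaks of any tests collected; it does not say how many men have results.

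**Step 3. What must hold for an event to be lost from the main table.** It must meet Section 10.1.1, be grade 3 or higher, be judged possibly, probably or definitely related (Sections 9.2.1 and 13.2.2), and be known only from these tests. Each condition shrinks the number.

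**Step 4. The plan's own safety figures.** Section 13.2.2 gives a 97% probability of observing a toxicity with a true rate of 5% in 71 treated patients, and a maximum 90% interval width of 21%.

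- At least one event: 1 − 0.95^71 = 0.974, which agrees with 97%.
- Maximum exact (Clopper-Pearson) 90% width over 0 to 71 events: 0.206, which agrees with 21%. The Wald version, 2 × 1.645 × √(0.25/71), is 0.195.

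Both figures presume that the toxicity is assessed in all 71 men. For an event visible only on the exempted glucose tests, the probability of its being counted under Section 9.2.1 is zero, whatever the true rate.

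**Step 5. Why the loss cannot be sized.** If m men were tested and the event rate is p, the chance of at least one event among them is 1 − (1 − p)^m. Neither input is in the documents, so both are assumed here. The 5% is the plan's generic illustration, not a hyperglycaemia rate.

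| m (assumed) | p = 1% | p = 5% |
|---|---|---|
| 10 | 0.10 | 0.40 |
| 20 | 0.18 | 0.64 |
| 35 | 0.30 | 0.83 |
| 71 | 0.51 | 0.97 |

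A range of 0.10 to 0.97 is too wide to support a statement of size. These figures also ignore the further conditions in Step 3 wherever p is not already restricted to events that meet them.

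**The case against.** The strongest reply has four parts.

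- **The definition already excludes most abnormal values.** A reader might infer that Section 10.2 turns every high glucose into an adverse event and that Section 9.2.1 therefore discards all laboratory hyperglycaemia. Section 10.1.1 does not support that: a value without symptoms, treatment or further tests is not an adverse event in the first place. This stands, and it limits the conflict to the values that qualify.
- **Other routes stay open.** History, examination, adverse event and medication review take place at each cycle visit (Section 8). Concomitant medications must be documented (Section 5.3.1.1). Serious events, including grade 4 events, have their own reporting duty (Section 10.4.1), which Section 9.2.1 does not mention. So it cannot be said that the trial would report no hyperglycaemia. This also stands.
- **The laboratory summary is not barred.** A reader might infer that Section 9.2.1 removes the glucose data from the Section 13.2.2 summary. It says only that they are not assessed for adverse events; a descriptive listing remains possible. Yet nothing requires one: Section 9.2.1 ties its laboratory assessments to the schedule in Section 8, which no longer lists glucose.
- **There may have been a good reason**, such as samples taken without fasting. The earlier amendments are not available, so this cannot be judged. Non-fasting collection would affect how a value is read, but would not by itself explain an exemption for a value that was acted on.

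None of this reconciles Section 9.2.1 with Section 10.1.1 for a value that led to treatment or further tests.

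**Conclusion.** The concern holds in a narrow form. Section 9.2.1 cannot be followed together with Sections 10.1.1 and 10.2 for the qualifying glucose values, no reason is documented, and the results concerned are the only glucose data the protocol provides for. The effect on the tabulated treatment-related grade 3 or higher events is probably small, given the number of conditions an event must meet, and its size cannot be derived from the documents.

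A reader might go further and infer that a claim of a better metabolic profile for enzalutamide would rest on this omission. The documents do not support that. Section 1.1 expects a better profile for hormone levels, quality of life and body fat. Glucose is not among those outcomes, nor among the secondary objectives in Section 1.3. The mention of metabolism in Section 2.3 is one undefined item in a list, and weight, skinfolds, waist circumference and bone markers are still measured.

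The conclusion assumes that at least some glucose results exist from after the start of treatment. If there are none, the sentence has no effect on the results and can simply be removed. The change is still worth making because it is cheap and the present rule selects safety data by analyte without explanation.

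**What to change.** 1. Delete the glucose sentence from Section 9.2.1.
2. Apply the Section 10.1.1 definition to the glucose values already collected. Do not turn values into adverse events on grade alone.
3. Grade those that qualify with the same CTCAE version as other laboratory events. The protocol names 4.03 in Section 9.2.1 and 4.0 in Section 10.2, so the one used should be stated. Assign attribution as for any other event.
4. In the Section 13.2.2 laboratory summary, list all collected glucose values descriptively, with the number of men tested as the denominator and fasting status where known.
5. Record in the protocol why glucose testing was stopped.

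The cost is one sentence and one review of existing values, with no new samples or visits. The downsides are a footnote on non-fasting samples, a denominator below 71 if not every man was tested, and possibly a slightly higher adverse event count.
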